10.2.3 Adverse Events of Special Interest

Adverse events of special interest (AESIs) will be composite events made up of TEAEs meeting the following MedDRA search strategies.

- GI events will include the MedDRA preferred terms (PTs) in the GI and GI procedure related events Company MedDRA Query (CMQ 80000145).

- POLY events will include the PTs in either the Peripheral Neuropathy Standard MedDRA Query (SMQ 20000034) broad search or Guillain-Barre Syndrome SMQ (SMQ 20000131) broad search.
- WEIGHT events will include the PTs in the Weight loss CMQ (CMQ 80000109).

For each AESI, the number and percentage of subjects experiencing one or more adverse events during the 26-week randomized Treatment Period will be summarized for each treatment group and for overall subjects by primary SOC and PT. Similar summaries will be prepared for all TEAEs that are not GI events as well as for all TEAEs that are in either the Peripheral Neuropathy Standard MedDRA Query (SMQ 20000034) narrow search or Guillain-Barre Syndrome SMQ (SMQ 20000131) narrow search.

10.2.4 Adverse Events by Subgroup

The number and percentage of subjects in each of the following subgroups experiencing one or more TEAEs during 26-week randomized Treatment Period will be summarized for each treatment group and for overall subjects by primary SOC and PT.

- Gender (male, female)
- Age category (< 65 years, ≥ 65 years)
- Baseline BMI category (< 25 kg/m², ≥ 25 kg/m²)
- Duration of Parkinson's disease (< 10 years, ≥ 10 years)

10.2.5 Listings of Adverse Events

The following additional summaries of adverse events will be prepared.

- Listing of all deaths for all subjects screened
- Listing of all serious TEAEs
- Listing of all TEAEs that led to discontinuation of study drug
- Listing of all GI AESIs (as defined in Section 10.2.3)
- Listing of all POLY AESIs (as defined in Section 10.2.3)

- Listing of all WEIGHT AESIs (as defined in Section 10.2.3)

10.3 Analysis of Laboratory Tests

Hematology variables include: partial thromboplastin time (PTT), hematocrit, hemoglobin, international normalized ratio (INR), mean corpuscular hemoglobin (MCHC), mean corpuscular volume (MCV), platelet count, prothrombin time (PT), red blood cell (RBC) count, white blood cell (WBC) count and WBC differentials.

Chemistry variables include: albumin, alkaline phosphatase, bicarbonate, total bilirubin, blood urea nitrogen (BUN), calcium, chloride, cholesterol, creatine phosphokinase (CPK), creatinine, gamma-glutamyl transpeptidase (GGT), glucose, lactate dehydrogenase (LDH), inorganic phosphorus, potassium, serum glutamic-oxaloacetic transaminase (SGOT/AST), serum glutamic pyruvic transaminase (SGPT/ALT), total protein, sodium, TSH, free T4, triglycerides and uric acid.

Urinalysis variables include: blood, glucose, ketones, pH, protein, specific gravity, and the results of microscopic analysis.

Special laboratory variables include: Vitamin B₁₂, Vitamin B₆, methylmalonic acid (MMA), folic acid and homocysteine levels.

10.3.1 Analysis of Mean Changes for Laboratory Tests

Analyses of mean change from baseline to each planned visit and to the minimum, maximum and final value during the 26-week randomized treatment period will be presented by treatment group for each continuous hematology, chemistry, urinalysis, and special laboratory variable.

For each change from baseline analysis, the following summary statistics for each treatment group will be presented: sample size, baseline mean, visit mean, and the mean, standard deviation, and median of the change from baseline. The baseline and visit means will be calculated for each visit for subjects who have both a baseline and visit value. The

mean changes for the LCIG group and for the OMT group during the 26-week randomized treatment period will be compared using an ANOVA with treatment as the factor. LS mean, standard error, 95% confidence interval and *P* value will be presented.

Analyses of mean change from the Extension/Transition Period baseline to each planned visit and to the minimum, maximum and final value during the Extension/Transition Period will be presented for each continuous hematology, chemistry, urinalysis, and special laboratory variable for OMT/LCIG subjects who enter the Extension/Transition Period.

10.3.2 Shifts Between Normal and Abnormal for Laboratory Tests

Laboratory observations will be categorized as normal, low, or high relative to the reference (normal) range associated with the laboratory that performed the assay. For each hematology, chemistry, urinalysis and special laboratory variable with a reference range, shift tables will be prepared by treatment group for reference range category shifts from baseline to lowest, highest and final value during the 26-week randomized treatment period. The tables will present:

- The numbers and percentages of subjects with low or normal observations at baseline who have a high observation at any post-baseline visit
- The numbers and percentages of subjects with normal or high observations at baseline who have a low observations at any post-baseline visit
- The numbers and percentages of subjects with low or normal observations at baseline who have a high observation at the final visit
- The numbers and percentages of subjects with normal or high observations at baseline who have a low observations at the final visit

No comparisons of treatment groups will be performed.

10.3.3 Potentially Clinically Significant (PCS) Laboratory Values

Criteria for potentially clinically significant (PCS) values have been predefined for selected laboratory variables as outlined in [Appendix F](#). For each variable, a summary of the number and percentage of subjects in each treatment group who have at least one post-baseline observation during the 26-week randomized treatment period that meets the PCS criteria and is more extreme than their baseline value will be provided.

A summary of the number and percentage of subjects who have at least one observation during the Extension/Transition Period that meets the PCS criteria and is more extreme than their Extension/Transition Period baseline value will be provided for OMT/LCIG subjects who enter the Extension/Transition Period.

A listing will also be prepared that will include, for each variable, all observations for each subject that met the PCS criteria for that variable at any time during the study. No comparisons of treatment groups will be performed.

10.4 Analysis of Vital Signs and Weight

Vital sign variables include: body temperature, pulse (sitting, standing and orthostatic), diastolic blood pressure (sitting, standing and orthostatic), and systolic blood pressure (sitting, standing and orthostatic).

Weight variables include: weight and BMI.

Orthostatic variables will be calculated as the change from sitting to standing (standing measurement minus sitting measurement).

BMI will be calculated using height as measured during screening.

10.4.1 Vital Sign and Weight Mean Changes

Analyses of mean change from baseline to each planned visit beginning with Day 7 and to the minimum, maximum and final value during the 26-week randomized treatment period will be presented by treatment group for each vital sign and weight variable. On the day

of the first LCIG infusion, orthostatic vital signs are to be collected at 0, 1, 2 and 3 hours post initial LCIG infusion start. Analyses of the mean change from pre-infusion baseline (planned time 0) to each post-infusion hourly time point will be presented for each vital sign variable other than body temperature for the LCIG group and subjects in OMT group entering Extension Period.

For each change from baseline analysis, the following summary statistics for each treatment group will be presented: sample size, baseline mean, visit (time point) mean, and the mean, standard deviation, and median of the change from baseline. The baseline and visit (time point) means will be calculated for each visit (time point) for subjects who have both a baseline and visit (time point) value. The mean changes during the 26-week randomized treatment period for the LCIG group and for the OMT group will be compared using an ANOVA with treatment as the factor. LS mean, standard error, 95% confidence interval and *P* value will be presented.

Analyses of mean change from the Extension/Transition Period baseline to each planned visit and to the minimum, maximum and final value during the Extension/Transition Period will be presented for each vital sign and weight variable for OMT/LCIG subjects who enter the Extension/Transition Period.

10.4.2 Shifts in BMI Category

BMI values will be categorized as low ($< 18.5 \text{ kg/m}^2$), normal (18.5 kg/m^2 to $< 25 \text{ kg/m}^2$), overweight (25 kg/m^2 to $< 30 \text{ kg/m}^2$) or obese ($\geq 30 \text{ kg/m}^2$). Shift tables will be prepared summarizing BMI category shifts from baseline to lowest, highest and final value during the 26-week randomized treatment period for each treatment group. No comparisons of treatment groups will be performed.

10.4.3 Potentially Clinically Significant (PCS) Vital Sign and Weight Values

Criteria for PCS values have been predefined for selected vital sign and weight variables as outlined in [Appendix F](#). For each variable, a summary of the number and percentage of

subjects in each treatment group who have at least one post-baseline observation during the 26-week randomized treatment period that meets the PCS criteria and is more extreme than their baseline value will be provided.

A summary of the number and percentage of subjects who have at least one observation during the Extension/Transition Period that meets the PCS criteria and is more extreme than their Extension/Transition Period baseline value will be provided for OMT/LCIG subjects who enter the Extension/Transition Period.

A listing will also be prepared that will include, for each variable, all observations for each subject that met the PCS criteria for that variable at any time during the study. No comparisons of treatment groups will be performed.

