Special Laboratory Tests ^o	X		X				X		X		X	X
Pregnancy Test ^p	X						X		X			
MIDI (Minnesota Impulsive Disorders Interview)	X	X	X				X	X	X	X	X	X
C-SSRS ^q	X	X	X				X	X	X	X	X	X
Adverse Events	X	X	X				X	X	X	X	X	X
Product Complaints							X	X	X	X	X	X
NMSS (Non-Motor Symptom Scale)			X					X	X	X		
PDSS-2 (Modified Parkinson's Disease Sleep Scale)			X					X	X	X		
UPDRS Parts I - V ^r	X		X					X	X	X	X	

Table 3. Study Activities (Continued)

Study Day (End of Week)	OMT/LCIG			Titration Visits	OMT/LCIG				LCIG V4 NJ/PEG-J Placement D1	LCIG Wk 17	LCIG Wk 22	OMT/LCIG Wk 26 or Premature Discontinuation	Wk 27 FU ^a	LCIG Transition to Commercial Visits ^b
	V1 Screening Wk -8/-4	V2 Screening Wk -1	V3 Randomization		Wk 2	Wk 6	Wk 12	Wk 17						
CGI-C (Clinical Global Impression of Change)												X		
PGIC												X		
PDQ-8 (Parkinson's Disease Questionnaire-8)			X		X							X		
MoCA (Montreal Cognitive Assessment)			X		X							X		
PAS (Parkinson Anxiety Scale)			X		X							X		
GDS-15 (Geriatric Depression Scale)			X		X							X		
King's PD Pain Scale			X		X							X		
Dose Titration Diary ^s									X					
Subject Dosing/Diary Completion									X			X		
LCIG System and Pump Training (Subject and Caregiver)			X					X						
OMT and LCIG Administration								X				X		
LCIG Titration								X				X		
Study Drug Prescription Record (LCIG group only)								X				X		
Removal of PEG-J													X ^t	
LCIG Cassettes Dispensed and/or Returned								X				X		X ^u

Table 3. Study Activities (Continued)

V = Visit; D = Day; FU = Follow-Up; Wk = Week

- a. Applicable only to LCIG subjects who prematurely discontinue LCIG treatment, or complete LCIG study treatment but will not transition to commercial LCIG.
- b. Applicable only to LCIG subjects who complete LCIG study treatment and will transition to commercial LCIG. Subjects will return every 6 weeks to return used LCIG cassettes and be dispensed cassettes. Safety assessments will be completed every 12 weeks until subjects' transition to commercial LCIG.
- c. Visit 2 is optional and is based on the Investigator's discretion of individual subject need during stabilization of anti-PD medications and medications to treat NMS.
- d. Visit 4 for LCIG Treatment (LCIGT) group only.
- e. Study-related assessments, procedures or activities may not occur prior to subject completing signed informed consent process.
- f. Update Medical/Neurological/PD History with any findings from Labs, Dermatologists, etc.

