Radiological Check of Tube Placement (LCIG Group Only)

Radiological check of NJ and PEG-J to determine correct location should occur prior to LCIG infusion initiation and prior to restart of LCIG post PEG-J placement. It can also be done at any time during treatment if indicated for worsening of Parkinsonian symptoms or non-responsiveness to extra doses.

PEG-Site (Stoma) Check (LCIG Group Only)

Following the PEG-J placement, site personnel will review proper after-care instructions and checking of the stoma instructions with the subject and/or care-partner as provided in the patient care materials/booklets.

After the initial PEG-J procedure, the PEG-J and stoma must be inspected by a gastroenterologist/proceduralist/surgeon/qualified radiologist (preferably the physician who placed the PEG-J), or their designated qualified personnel 2 – 7 days post PEG-J procedure.

Vital Signs/Weight

Body temperature, orthostatic vital signs and weight will be performed at the times indicated in [Table 3](#). All systolic and diastolic blood pressure and pulse rate measurements are to be measured orthostatically. Orthostatic systolic and diastolic blood pressure and pulse rate are to be measured while the subject is supine (after 3 to 5 minutes) and standing (after 2 minutes). Study staff should make efforts to measure with the same arm and method including recording of arm and method in the subject's source documentation.

On the day of the first LCIG infusion, orthostatic vital signs should be obtained at 0, 1, 2 and 3 hours post initial LCIG start. An attempt should be made to obtain all other vital signs at a consistent time of day. Vital signs should be repeated when PEG-J inserted.

Vital signs will include body weight will be measured at the times indicated in [Table 3](#). The subject will wear lightweight clothing and no shoes during weighing.

Height

Height will be measured only at V1; the subject will not wear shoes.

12-Lead Electrocardiogram (ECG)

A single 12-lead resting ECG will be obtained at study visits indicated in [Table 3](#). An attempt should be made to obtain all other ECGs at a consistent time of day.

ECGs will be recorded after the subject has been supine for at least 5 minutes. The subject should be instructed to remain completely stationary during the recording, without talking, laughing, deep breathing or swallowing during the time of recording (10 seconds).

ECG Data Review

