4.2 Design Diagram

This is a Phase 3b, open-label, randomized multicenter 26-week study comparing LCIG to OMT for the treatment of non-motor symptoms in subjects with advanced Parkinson's disease.

The study will consist of three sequential parts:

Part 1: Screening period. The screening period will consist of three visits, Visit 1 (V1), Visit 2 ([V2] [optional]) and the Randomization Visit (V3) in which the subject will be assessed to determine eligibility. The duration of the Screening Period can be between 30 – 67 days to accommodate the required procedures, training and collection of diaries, and to allow for stabilization of anti-PD medications and medications to treat NMS. All anti-PD medications and medications to treat NMS are required to be stable for a minimum of 30 days prior to randomization.

Part 2: Treatment period. Those subjects randomized to OMT at the end of V3 will remain on their current optimized regimen. The day after randomization will be considered Day 1 of their treatment period and subjects will have study visits at the end of Weeks 2, 6, 12, and 26. All subjects randomized to the LCIG group should have all anti-PD medications, with the exception of levodopa formulations, tapered off within 14 days after randomization. Optional nasojujunal and/or percutaneous endoscopic gastrostomy with a jejunal tube (PEG-J) placement will then be placed. After that, the subject may begin initiation and titration of LCIG infusion to be adjusted to obtain the optimal clinical response in 14 days. The day of initial NJ or PEG-J placement will be considered Day 1 for subjects in the LCIG group. Study visits happen at the end of Weeks 2, 6, 12, and 26.

Part 3: Extension Period. Subjects in the United States or South Korea from both treatment arms who complete the 26 week study may continue into the Extension Period of the study. South Korea subjects in the LCIG arm will have study drug dispensation every 4 weeks and will have study visits every 6 months. South Korea subjects from the OMT arm will undergo the NJ (optional) and PEG-J procedures, titration, plus have visits at 2 weeks, 6 weeks, 3 months and 6 months post NJ or PEG-J. Subjects will then continue to receive study drug every 4 weeks and will have study visits every 6 months until Duodopa is commercially available.

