6.5 Analysis of Vital Signs by Planned Time

Vital sign measurements were to be performed at hourly intervals on the first day of LCIG infusion via NJ and via PEG-J. Observations on the first day of LCIG infusion will be assigned to a planned time based on the time of assessment relative to the reported start time of the first LCIG infusion as follows.

Table 5. Analysis Windows for Vital Signs on the Day of LCIG Infusion for the LCIG Group

Planned Time	Nominal Relative Time (Minutes)	Relative Time Range (Minutes)
Hour 0	0	≤ 0
Hour 1	60	> 0 – 90
Hour 2	120	91 – 150
Hour 3	180	> 150

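### The by-arm PCS vital-sign table counts any single post-baseline reading, but for blood pressure and pulse LCIG subjects have 8 to 12 scheduled readings against 4 for OMT

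*SAP*

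**What the plan says.** **Counting rule.** SAP 10.4.3 reports, by arm, counts and percentages for "subjects in each treatment group who have at least one post-baseline observation during the 26-week randomized treatment period that meets the PCS criteria", provided the value is also more extreme than baseline. The section sets no limit by visit and no averaging rule. It adds a listing of every qualifying observation and states that the arms will not be formally compared.

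**Baseline.** SAP 6.3 fixes baseline at the last value on or before the day of randomization.

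**Schedule.** SAP 4.2 says of OMT that "subjects will have study visits at the end of Weeks 2, 6, 12, and 26". LCIG subjects have visits at the same weeks. Protocol Table 3 adds "Visit 4 for LCIG Treatment (LCIGT) group only". On the first infusion day, per SAP 10.4.1, "orthostatic vital signs are to be collected at 0, 1, 2 and 3 hours post initial LCIG infusion start". SAP 6.5 goes further: "Vital sign measurements were to be performed at hourly intervals on the first day of LCIG infusion via NJ and via PEG-J". Protocol 5.3.1.1 says only "Vital signs should be repeated when PEG-J inserted", without saying whether that means one reading or the hourly set.

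**Related analysis.** SAP 10.4.1 also analyses mean change "to the minimum, maximum and final value during the 26-week randomized treatment period" and compares the arms by ANOVA with a P value.

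**Averaging.** SAP 6.4 averages same-day values when it assigns observations to planned visits. Protocol 8.1.4.4 ties same-day averaging to the mean-change analysis; its PCS paragraph has no such rule.

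**The concern.** A statistic of the form any qualifying reading grows with the number of readings taken. Because baseline is fixed at randomization, every infusion-day reading in the LCIG arm is post-baseline, including hour 0, which is taken before the drug can act. OMT has no matching day. The two percentages in the table therefore summarise different amounts of observation.

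What is at stake is how the blood pressure and pulse rows are read. The table puts the arms side by side, and readers will compare the percentages whether or not a test is attached. If the LCIG figure is higher, the table alone cannot show how much comes from treatment and how much from more frequent measurement. The minimum and maximum in SAP 10.4.1 depend on the number of readings in the same way, and there a P value is attached.

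**Working it through.** The plan gives no figure to reproduce here, so the check counts readings and then asks what the counts imply.

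**Step 1: scheduled post-baseline readings (blood pressure, orthostatic blood pressure, pulse).**
- OMT: Weeks 2, 6, 12, 26 = 4.
- LCIG, direct PEG-J: 4 + 4 hourly (0, 1, 2, 3 h) = 8.
- LCIG, NJ then PEG-J, with the second hourly series of SAP 6.5: 4 + 4 + 4 = 12.
- LCIG, NJ then PEG-J, if the protocol's repeat is one reading: 4 + 4 + 1 = 9.

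A Week 27 reading, possible for some LCIG subjects, is left out. Weight is not in the hourly set, and SAP 10.4.1 excludes temperature from the hourly analysis, so these counts do not apply to those rows.

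**Step 2: chance of at least one flag, equal per-reading risk p in both arms, independent readings.** The formula is 1 − (1 − p)^k. The value of p is an assumption, since the documents do not give it.

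| p | OMT, k = 4 | LCIG, k = 8 | LCIG, k = 9 | LCIG, k = 12 |
|---|---|---|---|---|
| 1% | 3.9% | 7.7% | 8.7% | 11.4% |
| 2% | 7.8% | 14.9% | 16.6% | 21.5% |
| 5% | 18.5% | 33.7% | 37.0% | 46.0% |
| 10% | 34.4% | 57.0% | 61.3% | 71.8% |

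At p = 5% the LCIG/OMT ratio is 33.7/18.5 = 1.8 for 8 readings and 46.0/18.5 = 2.5 for 12.

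**Step 3: correlated readings, p = 5%.** Readings within a person, above all within three hours, are not independent. With a latent-normal model:

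| Assumed correlation | OMT (4) | LCIG (8) | LCIG (12) | Ratios |
|---|---|---|---|---|
| 0.3 throughout | 16.4% | 26.7% | 34.2% | 1.6, 2.1 |
| 0.5 throughout | 14.4% | 21.9% | 27.0% | 1.5, 1.9 |
| 0.5 between days, 0.8 within a day | 14.4% | 19.9% | 24.2% | 1.4, 1.7 |
| 0.9 throughout | 8.8% | 10.9% | 12.1% | 1.2, 1.4 |

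The direction is the same in every row. Only perfectly correlated readings would close the gap.

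**Step 4: if the SAP 6.4 averaging applied to PCS.** The counts become 5 (one infusion day) or 6 (two) against 4. At p = 5% and independence, this gives 22.6% or 26.5% against 18.5%, so ratios of 1.2 and 1.4. The imbalance is smaller, but an orthostatic systolic drop of 30 mmHg or more at one hour (SAP Appendix G) could be averaged below the threshold.

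**Step 5: change to minimum in SAP 10.4.1, no drug effect.** The assumptions are 44 per arm, normal readings, a single-reading baseline, and within-subject SD of 8 to 12 mmHg. Each pair gives one hourly series, then two.

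| Share of within-subject variance common to a day | False-positive rate, no averaging | False-positive rate, same-day averaging |
|---|---|---|
| 0 | 32%, 65% | 5%, 6% |
| 0.5 | 22%, 50% | 6%, 10% |
| 0.8 | 15%, 34% | 8%, 13% |

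With independent readings, the spurious difference is about 3 to 7 mmHg without averaging and about 0.4 to 0.9 mmHg with it.

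**The case against.** The strongest reply is that the table is descriptive. SAP 10.4.3 plans no comparison of arms, so no P value or conclusion rests on it. That stands, and it limits the harm to presentation.

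Second, a reader might infer that a true LCIG effect could never be told apart from extra measurement. The documents do not support that. The planned listing shows each qualifying observation, and SAP 10.4.1 plans an hourly change-from-pre-infusion summary, so infusion-day flags can be identified. What is missing is a comparable rate.

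Third, the SAP may not mean every raw reading. If PCS used only windowed visit values, a first infusion on Day 1 would fall in no window of SAP Table 2 (Week 2 starts at Day 2), and the arms would be nearly equal. If same-day averaging applied, the counts would be 5 to 6 against 4. Either is possible, but 10.4.3 states neither, and its literal wording takes any observation.

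Fourth, it is tempting to read the ANOVA of minimum and maximum as carrying a false-positive rate of a third to two thirds. That needs independent readings and no averaging. For mean change, the protocol and SAP 6.4 point to averaging, so it is the less supported reading.

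Fifth, orthostatic hypotension is not among the adverse events of special interest in protocol 6.1.1.3, and any inflation counts against the sponsor's own product. Both are true. Neither makes the two percentages comparable.

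**Conclusion.** The concern holds for blood pressure, orthostatic blood pressure and pulse. Taken literally, SAP 10.4.3 gives an LCIG subject 8 chances to be flagged (direct PEG-J) or about 9 to 12 (via NJ) against 4 for OMT, so the LCIG percentage is expected to be higher with no drug effect. The upper count of 12 needs the optional NJ route and the SAP 6.5 wording.

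The size cannot be derived from the documents. At an assumed 5% per reading, the LCIG/OMT ratio is about 1.8 to 2.5 under independence and about 1.2 to 1.9 for correlations of 0.5 to 0.9. A doubling or more should not be taken as the expected result, because independence is implausible for four readings in three hours.

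The consequence is a misleading side-by-side percentage, not a false test result. The minimum/maximum ANOVA in SAP 10.4.1 is affected materially if same-day values are not averaged. If they are averaged the effect is slight in most cases, though the simulated error rate reached about 13% with two hourly series and strongly similar same-day readings.

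**What to change.** - In SAP 10.4.3, base the by-arm PCS summary for blood pressure and pulse on the visits common to both arms (Weeks 2, 6, 12, 26), with one value per visit.
- In SAP 10.4.1, base the minimum and maximum comparison on the same values.
- Report PCS from the individual, unaveraged hourly readings on the infusion days in a separate LCIG-only table, beside the hourly summary already planned in SAP 10.4.1.
- State whether the same-day averaging of SAP 6.4 applies to each table. Reconcile SAP 6.5 with protocol 5.3.1.1 on whether the PEG-J repeat is one reading or the hourly set.
- An all-observation PCS table may be kept as a supplement if it is labelled with the unequal number of readings per arm.
- In the same edit, correct the cross-reference in SAP 10.4.3: it points to Appendix F (laboratory values), while the vital-sign criteria are in Appendix G.

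The cost is a few lines of SAP text and one extra table. No new data are needed, and no safety information is lost.
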